In the 1960s, a formalin-inactivated (FI) RSV vaccine was associated with enhanced respiratory disease (ERD) in young children, characterized by an increased rate of RSV-mediated, severe lower respiratory tract infection in the vaccinated individuals compared with the control group. 0,0,0,0 Although the mechanisms for ERD are not fully understood, it is thought that the FI-RSV vaccine may have: 1) failed to induce adequate neutralizing antibody titers; 2) led to an overproduction of binding antibodies promoting immune complex deposition and hypersensitivity reactions; 3) failed to induce adequate numbers of memory CD8⁺ T cells important for viral clearance; and 4) induced a T helper cell (Th) type 2-skewed type T-cell response. Vaccineinduced ERD has also been described for SARS-CoV and MERS-CoV in some animal models in which candidate vaccines induced a Th2 biased immune response, 0,0,0,0,0 but proof of human SARS-CoV or MERS-CoV vaccine-associated enhanced disease does not exist as these candidate vaccines were never tested for efficacy nor used in outbreak situations. For SARS and MERS, the mechanism of enhanced disease observed in mice has been associated with a Th2-mediated eosinophilic infiltration in the lung, which is reminiscent of ERD effects observed after RSV infection of mice immunized with FI-RSV. Similar to RSV vaccines, enhanced disease has been shown for whole-inactivated SARS-CoV vaccines, as well as subunit vaccines inducing a Th2type immune response, which can be rescued by formulating vaccines in Th1-skewing adjuvants. In addition to a Th1-biased immune response, also induction of a high proportion of neutralizing antibodies compared with virus binding antibodies is desirable to prevent predisposition to enhanced disease as observed for RSV vaccines. While vaccine-associated enhanced disease was observed in nonclinical studies with experimental SARS and MERS vaccines, it is not a given that the same risk applies to COVID-19 vaccines. To the sponsor's knowledge, antibody-related COVID-19 disease enhancement has not been observed in nonclinical models yet. Antibodies against the receptor-binding domain (RBD) of SARS-CoV-2 were shown not to enhance in vitro infectivity. Repeated SARS-CoV-2 challenge of NHP or NHP studies with Th2 biasing COVID-

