9.4.2. Primary/Secondary Endpoints

Immunogenicity Endpoints

Descriptive statistics (geometric mean and confidence intervals, or median and interquartile range Q1-Q3, as appropriate) will be calculated for continuous immunologic parameters. Several definitions of serological response will be applied (fold increases in GMT [VNA] or GMC [ELISA]). Graphical representations of immunologic parameters will be made as applicable. Frequency tabulations will be calculated for discrete (qualitative) immunologic parameters, as applicable.

In addition, the ratio between neutralizing and binding antibodies as determined by VNA and S protein ELISA, respectively, will be calculated together with confidence intervals.

For adults, all data will be analyzed separately from the point of unblinding for safety and immunogenicity. Details will be described in the SAP.

For adolescents, limited pooled safety and reactogenicity data (planned for IDMC review) and group unblinded immunogenicity data (summary of S-ELISA, including GMC, and seroresponse rates for all participants and seronegative at baseline participants, in Ad26.COV2.S 2.5x10¹⁰ vp only) were reviewed by the sponsor prior to Amendment 6 (see Section 4.1 Overall Design).

The immunogenicity analyses will be performed on the PPI population. Immunogenicity analyses will also be done on the FAS (participants who became infected during the study will be analyzed as a subgroup and shown in the graphs using different colors and symbols).

Safety Endpoints

No formal statistical testing of safety data is planned. Safety data will be analyzed descriptively by vaccine group. In addition, for selected tables, tabulations pooled by vaccine dose will also be provided. All safety analyses will be done on the FAS.

Adverse Events

The verbatim terms used in the eCRF by investigators to identify AEs will be coded using the Medical Dictionary for Regulatory Activities (MedDRA). All reported AEs will be included in the analysis. (S)AEs caused by molecularly confirmed SARS-CoV-2 infection will be removed at the analysis level from the (S)AE listings and tables and presented separately. For each AE, the percentage of participants who experience at least one occurrence of the given event will be summarized by vaccine group.

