5.7.1.2. Handling of Missing and/or Unquantifiable Immune Response Data

Missing immune response data will not be imputed.

Values below the lower limit of quantification (LLOQ) or limit of detection (LOD) will be handled as follows:

- Calculation of geomean and median:
 - o values <LLOQ are imputed with LLOQ/2.
- Calculation of fold increases from baseline:
 - o values <LLOQ are imputed with LLOQ.

Values above the upper limit of quantification (ULOQ) will be handled as follows:

- Calculation of geomean and median:

- o Values >ULOQ are imputed with ULOQ.
- Calculation of fold increases from baseline:
 - o Values >ULOQ are imputed with ULOQ.

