The ratio of binding antibodies (S-ELISA) to wild type VNA, and the ratio of binding antibodies (S-ELISA) to pseudovirion expressing S protein VNA will be calculated for each time point. Values <LLOQ will be imputed with LLOQ for the calculation of the ratios. In addition, the ratio of the fold increase from baseline in binding antibodies (S-ELISA) to the fold increase from baseline in wild type VNA, and the ratio of the fold increase from baseline in binding antibodies (S-ELISA) to the fold increase from baseline in pseudovirion expressing S protein VNA will be calculated for each post-baseline time point. Values <LLOQ will be imputed with LLOQ for the calculation of the fold increase ratios. The following statistics will be calculated and tabulated: N, geometric mean and corresponding 95% CI of the ratio. Graphical displays will also be prepared, showing – for each time point – the geometric mean of the ratio and its 95% CI, together with the individual data points (dot plot).

If a similar assay is performed at different analyzing labs, then separate statistical analyses may be performed.

Scatterplots between humoral assay results will be provided for selected time points. These may include but are not limited to:

- Binding antibodies (S-ELISA) versus wild type VNA
- Binding antibodies (S-ELISA) versus pseudovirion expressing S protein VNA
- Wild type VNA versus pseudovirion expressing S protein VNA

If a similar assay is performed at different analyzing labs, then the statistical analyses may distinguish between these and provide separate scatterplots for each analyzing lab versus the other assay of interest. These scatterplots will display the values as analyzed for the geometric mean calculations, with values <LLOQ imputed with LLOQ (if an LLOQ is defined) and values >ULOQ imputed with ULOQ (if an ULOQ is defined). The LLOQ and ULOQ cut-off values per assay will be visualized in the scatterplots. Spearman correlation coefficients will also be provided (one per scatterplot).

In addition, results for group 4 (High Dose single vaccination) and lower doses with double vaccination (D56 regimen) will be graphically presented and summarized with descriptive statistics.

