5.7.1.5.2. Cellular assays

For ICS, if available, following statistics will be calculated: N, median, first and third quartile, minimum and maximum of the actual values, number and percentage of participants with a positive (if available). Additional statistics may be calculated and will be detailed in the DPS.

It is planned to analyze the following cell populations at the time of the first interim analysis. The DPS may provide an updated version of this list, e.g. for subsequent analyzes.

- CD4+:
 - IFN-g or IL2
 - IFN-g or IL2 NOT TH2
 - IL4 and CD40L
 - IL4 or IL5 or IL13 and CD40L
- CD8+:
 - IFN-g or IL2

The data received from the analyzing lab(s) will contain background subtracted values (“Immediately reportable values”; i.e. background subtracted^a percentage of cells expressing the cytokine or cytokine combination). Negative background subtracted values will be imputed with zero prior to further processing.

The data will contain a positivity call for each cell population. Sample positivity should therefore not be further derived at the statistical analysis stage.

Tables will be provided that show the descriptive statistics mentioned above, structured as follows: CD4+/CD8+, peptide pool (as available in the database, e.g. SARS-Cov2-S, SARS-Cov2-S, SARS-Cov2-S1, SARS-Cov2-S2), cytokine (combination), and time point.

^a Also known as “mock subtracted”

Participant profiles of the actual values over time will be graphically presented. For the graphs, original values will be displayed on the log₁₀ scale, with values <0.022% imputed with 0.011% (only for visual representation; calculations will be based on the actual values). The graphs that show individual participants data will visually differentiate between positive/negative samples (e.g. different symbols and/or different colors)

The reported values are percentage of cells expressing the cytokine(s).

Assessment of TH1/Th2 response ratio

Based on the combined SARS-Cov2-S peptide pool, and using post baseline time points only, a Th1/Th2 response ratio will be calculated for samples that satisfy at least one of the following two conditions:

- a Th1 response (“IFN-g or IL2 NOT TH2”) that is both positive and $\geq 2 \times$ LLOQ,

or

- a Th2 response (“IL4 or IL5 or IL13 and CD40L”) that is both positive and $\geq 2 \times$ LLOQ

For the purposes of the Th1/Th2 ratio analysis, the LLOQ is 0.022% for both cell populations (Th1 and Th2).

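### The S-ELISA/VNA ratio sets values below the LLOQ to the LLOQ with no evaluability rule, so it is a lower bound for binding-only samples and an assay constant for double negatives

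*SAP*

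**What the plan says.** Protocol 9.4.2 states that "the ratio between neutralizing and binding antibodies as determined by VNA and S protein ELISA, respectively, will be calculated together with confidence intervals". SAP 5.7.1.5.1 implements this as S-ELISA divided by wild-type VNA and S-ELISA divided by pseudovirion VNA. For the latter the text reads "pseudovirion expressing S protein VNA will be calculated for each time point". The rule for low values is "Values <LLOQ will be imputed with LLOQ for the calculation of the ratios", and the summary is "N, geometric mean and corresponding 95% CI of the ratio", with a dot plot.

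The same section adds a ratio of fold increases from baseline at each post-baseline time point, with a matching rule: "Values <LLOQ will be imputed with LLOQ for the calculation of the fold increase ratios". Neither ratio has a stated condition on positivity, time point or arm.

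Three other places bear on this:

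- SAP 5.7.1.2, for geometric means and medians: "values <LLOQ are imputed with LLOQ/2". For fold increases it uses the LLOQ itself.
- SAP 5.7.1.5.2, for the cellular ratio: "a Th1/Th2 response ratio will be calculated for samples that satisfy at least one of the following two conditions". Only post-baseline samples count, at least one response must be positive and at least twice the LLOQ, and one-sided results are reported as above or below 1.
- Protocol 2.2, on predisposition to enhanced disease: "induction of a high proportion of neutralizing antibodies compared with virus binding antibodies is desirable". A low S-ELISA/VNA ratio is therefore the favourable one.

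**The concern.** A sample with measurable binding and undetectable neutralisation has the least favourable profile this ratio can describe. Setting its VNA to the LLOQ gives that sample the largest denominator consistent with an undetectable result, and so the smallest possible ratio. The more such samples a regimen, age group or time point has, the more its geometric mean is pulled towards the favourable side. The study is meant to explore how responses vary with dose and interval, so a bias that varies with the share of undetectable values can blur the descriptive comparisons this table invites.

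Samples negative in both assays carry no information on the balance of binding and neutralisation. They still enter the geometric mean with an apparently precise value.

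**Working it through.** The plan states no figure for this ratio, so there is nothing to reproduce. Write E and V for the S-ELISA and VNA values, and LE and LV for their LLOQs.

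**What the rule does to each kind of sample (algebra only)**

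| S-ELISA | VNA | Reported ratio | Effect |
|---|---|---|---|
| above LE | above LV | E/V | correct |
| above LE | below LV | E/LV | too low, since V < LV |
| below LE | below LV | LE/LV | constant, not a measurement |
| below LE | above LV | LE/V | too high |

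In the second row the ratio is understated 2-, 4- or 10-fold if the true VNA is 0.5, 0.25 or 0.1 times LV. In the third row, a set made up entirely of such samples has SD 0 and a confidence interval of zero width. LE/LV is never above the E/LV of a binding-only sample, so double negatives dilute that pattern. Relative to samples positive in both assays, their effect can go either way, depending on LE/LV.

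**Fold-increase ratio, both baselines below LLOQ**

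(E/LE)/(V/LV) = (E/V) × (LV/LE). This is the plain ratio times one constant, so between-group contrasts are the same as for the plain ratio. The level moves with the limits, and SAP 5.7.1.3 expects those to change, with retrospective application, if an assay goes from qualified to validated.

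**Size of the bias in a group geometric mean**

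Assumptions, none of them from the documents: log10 VNA is normal with SD 0.45; the log10 ratio is independent of VNA with SD 0.25; the true ratio is the same in all groups; a share q of VNA values is below LV. Flooring a normal variable at its q-quantile z raises its mean by SD × k(q), where k(q) = q·z + φ(z).

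- VNA floored, S-ELISA always quantifiable: reported/true = 10^(−0.45·k(q)).
- S-ELISA also floored, at share q/2: its SD is √(0.45² + 0.25²) = 0.515, and reported/true = 10^(0.515·k(q/2) − 0.45·k(q)).
- Undetectable-VNA samples alone (S-ELISA quantifiable): 10^(−0.45·k(q)/q).
- LLOQ/2 for VNA (S-ELISA quantifiable): 10^(−0.45·k(q) + q·log10 2).

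| q | k(q) | VNA floored | Both floored | Undetectable samples only | LLOQ/2 rule |
|---|---|---|---|---|---|
| 10% | 0.0473 | 0.952 | 0.976 | 0.61 | 1.02 |
| 20% | 0.1116 | 0.891 | 0.942 | 0.56 | 1.02 |
| 30% | 0.1904 | 0.821 | 0.900 | 0.52 | 1.01 |
| 40% | 0.2850 | 0.744 | 0.850 | 0.48 | 0.98 |

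Simulation of 400,000 pairs agrees to within rounding. The understatement is therefore about 2–11% at 10–20% below LLOQ and 10–26% at 30–40%.

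**A second set of assumptions**

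Here both log10 SDs are 0.45, the correlation is 0.7 and LE/LV = 1, with 48% of samples binding-only and 2% double-negative. The true geometric mean ratio is 7.99. The SAP rule gives 5.32 and LLOQ/2 gives 7.42. The binding-only samples have a true geometric mean of 10.72 but are reported at 4.89, below the overall reported mean. The least favourable samples look better than average.

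**The case against.** The strongest reply is that little depends on this ratio. It appears under the primary/secondary heading of Protocol 9.4.2 but is not a listed endpoint in Protocol 3 or in SAP 5.3 to 5.5. No hypothesis is tested, and harm monitoring in SAP 5.7.2 uses COVID-19 case counts. Protocol 2.2 itself says the enhanced-disease risk may not apply to COVID-19 vaccines. All of this stands and sets the severity.

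A reader might infer that the plan conceals an enhanced-disease signal or could distort a decision. The documents do not support that. Positivity and responder status are defined for each assay, and S-ELISA/VNA scatterplots with the limits drawn are planned for selected time points. What remains missing is the joint count of binding-positive, VNA-undetectable samples at every time point.

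Other replies:

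- Using the LLOQ follows the SAP's own fold-increase convention. True, but the summary here is a geometric mean, for which the SAP uses LLOQ/2.
- The bias is within sampling error. With SD 0.25 and n = 75, the 95% limits are a factor of 10^(±1.96 × 0.25/√75), or 0.88 to 1.14. That covers the lower shares, but the bias does not average out over groups or time points.
- The Data Presentation Specifications may add rules. They may; the inclusion of double negatives is read from the absence of any restriction. The LLOQ substitution itself is explicit.
- LLOQ/2 is also arbitrary and leaves double negatives at LE/LV. Correct, so an evaluability rule is needed as well.

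**Conclusion.** The point holds as a low-severity defect in a descriptive statistic. The substitution rule and the absence of an evaluability condition are in the text. That the ratio is a lower bound for binding-only samples and a constant for double negatives follows by algebra. The size does not: the 2–26% range rests on assumed SDs and on assumed shares below LLOQ of 10–40%.

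Three stronger readings should be resisted:

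- **That the rule always biases in the reassuring direction.** Samples with detectable VNA and S-ELISA below LLOQ go the other way. They were about 0–1% of samples under the second set of assumptions, but the documents give no share.
- **That the fold-increase ratio is biased by its baseline imputation.** With both baselines below LLOQ it is redundant and its level is set by the assay limits, but between-group contrasts are unaffected by that constant.
- **That every baseline and placebo value is the same constant.** Exclusion of screening positives makes this likely for most. The documents do not say that the screening serology is the study S-ELISA, and placebo participants infected later stay in the full analysis set.

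**What to change.** Amend SAP 5.7.1.5.1:

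1. As is already done in spirit for Th1/Th2, compute the ratio only for post-baseline samples with S-ELISA above LLOQ, and report the number evaluable.
2. For VNA below LLOQ, use LLOQ/2 (the SAP's geometric-mean rule) or treat the ratio as censored above E/LLOQ. Keep the present LLOQ rule as a sensitivity analysis.
3. Tabulate, by regimen and time point, the number and percentage with S-ELISA above LLOQ and VNA at or below LLOQ.
4. Drop the fold-increase ratio, or footnote that its level depends on the two LLOQs. Do not restrict it to quantifiable baselines: screening positives are excluded, so almost no participants would remain.

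This needs wording and minor programming, and no new data. The price is fewer samples in the ratio tables, including the loss of any with detectable VNA but S-ELISA below LLOQ, and a ratio that may look less favourable.

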5.7.1.5.2. Cellular assays

For ICS, if available, following statistics will be calculated: N, median, first and third quartile, minimum and maximum of the actual values, number and percentage of participants with a positive (if available). Additional statistics may be calculated and will be detailed in the DPS.

It is planned to analyze the following cell populations at the time of the first interim analysis. The DPS may provide an updated version of this list, e.g. for subsequent analyzes.

- CD4+:
 - IFN-g or IL2
 - IFN-g or IL2 NOT TH2
 - IL4 and CD40L
 - IL4 or IL5 or IL13 and CD40L
- CD8+:
 - IFN-g or IL2

The data received from the analyzing lab(s) will contain background subtracted values (“Immediately reportable values”; i.e. background subtracted^a percentage of cells expressing the cytokine or cytokine combination). Negative background subtracted values will be imputed with zero prior to further processing.

The data will contain a positivity call for each cell population. Sample positivity should therefore not be further derived at the statistical analysis stage.

Tables will be provided that show the descriptive statistics mentioned above, structured as follows: CD4+/CD8+, peptide pool (as available in the database, e.g. SARS-Cov2-S, SARS-Cov2-S, SARS-Cov2-S1, SARS-Cov2-S2), cytokine (combination), and time point.

^a Also known as “mock subtracted”

Participant profiles of the actual values over time will be graphically presented. For the graphs, original values will be displayed on the log₁₀ scale, with values <0.022% imputed with 0.011% (only for visual representation; calculations will be based on the actual values). The graphs that show individual participants data will visually differentiate between positive/negative samples (e.g. different symbols and/or different colors)

The reported values are percentage of cells expressing the cytokine(s).

Assessment of TH1/Th2 response ratio

Based on the combined SARS-Cov2-S peptide pool, and using post baseline time points only, a Th1/Th2 response ratio will be calculated for samples that satisfy at least one of the following two conditions:

- a Th1 response (“IFN-g or IL2 NOT TH2”) that is both positive and $\geq 2 \times$ LLOQ,

or

- a Th2 response (“IL4 or IL5 or IL13 and CD40L”) that is both positive and $\geq 2 \times$ LLOQ

For the purposes of the Th1/Th2 ratio analysis, the LLOQ is 0.022% for both cell populations (Th1 and Th2).

If both cell populations (Th1 and Th2) are positive and $\geq 2 \times$ LLOQ, then the ratio of Th1/Th2 will be calculated as a numerical result.

If only one cell population (either Th1 or Th2) is positive and $\geq 2 \times$ LLOQ, then the following rules will be used to determine a qualitative assessment of the Th1/Th2 ratio

- If one cell population is positive and the other is negative, then the positive cell population is greater than the negative cell population: if the Th1 response is positive and the Th2 response is negative, then the Th1/Th2 ratio will be set to “>1”. If the Th1 response is negative and the Th2 response is positive, then the Th1/Th2 ratio will be set to “<1”

- If both cell populations are positive, then the cell population that is $\geq 2 \times$ LLOQ is greater than the cell population that is $< 2 \times$ LLOQ: if the Th1 response is $\geq 2 \times$ LLOQ and the Th2 response is $< 2 \times$ LLOQ, then the Th1/Th2 ratio will be set to “>1”. If the Th1 response is $< 2 \times$ LLOQ and the Th2 response is $\geq 2 \times$ LLOQ, then the Th1/Th2 ratio will be set to “<1”.

For each post baseline time point, the number of participants with an evaluable Th1/Th2 response ratio will be tabulated, together with the number and percentage of participants with a Th1/Th2 ratio ≥ 1 and the number and percentage of participants with a Th1/Th2 ratio < 1 . Graphical display(s) of these data may also be produced.

Further details and/or updated rules will be provided in the DPS.

5.7.1.6. Statistical modeling of the immune responses

The VNA and ELISA results at D14 and D28 post 1st Vaccination and post 2nd Vaccination will be used to investigate potential dose-response effects. For the D28 post 2nd Vaccination also a potential interval duration effect between the two vaccinations will be explored.

In all modeling approaches the VNA and ELISA data will be log10 transformed.

All modeling exercises are explorative in nature and not powered for formal hypothesis testing.

5.7.1.6.1. Dose response modeling

To explore the dose effect of single vaccination, data from D14 post 1st Vaccination of the groups 1-10 will be analyzed using a regression model with log10 transformed VNA and ELISA results as dependent variable and dose as exploratory variable. Depending on the pattern observed a linear or non-linear model will be used.

To explore the dose effect of single vaccination, data from D28 post 1st Vaccination of the groups 1-10 will be analyzed using a regression model with log10 transformed VNA and ELISA results as dependent variable and dose as exploratory variable. Depending on the pattern observed a linear or non-linear model will be used.

To explore the dose effect of the 56day double vaccination regimen, data from D28 post 2nd Vaccination of the groups 1:3, and 6 will be analyzed using a regression model with log10 transformed VNA and ELISA results as dependent variable and dose as exploratory variable. Depending on the pattern observed a linear or non-linear model will be used.

To explore the dose effect of the 56day single vaccination regimen, data from D28 post 2nd Vaccination of the groups 4:5, and 6 will be analyzed using a regression model with log10 transformed VNA and ELISA results as dependent variable and dose as exploratory variable. Depending on the pattern observed a linear or non-linear model will be used.

Depending on the observed data pattern, the placebo groups may be excluded from the analysis and focus set only on the dose response relationship within the active doses studied.

